#### *Special notes on the assessment of target lesions*

- Lymph nodes: Lymph nodes identified as target lesions should always have the actual short axis measurement recorded and should be measured in the same anatomical plane as the baseline examination, even if the nodes regress to below 10 mm on study. This means that when lymph nodes are included as target lesions, the ‘sum’ of lesions may not be zero even if complete response criteria are met, since a normal lymph node is defined as having a short axis of < 10 mm.
- Target lesions that become ‘too small to measure’: All lesions (nodal and non-nodal) recorded at baseline should have their actual measurements recorded at each subsequent evaluation, even when very small (e.g., 2 mm). If the radiologist is able to provide an actual measure, that should be recorded, even if it is below 5 mm.

However, when such a lesion becomes difficult to assign an exact measure to then:

- (i) if it is the opinion of the radiologist that the lesion has likely disappeared, the measurement should be recorded as 0 mm.
- (ii) if the lesion is believed to be present and is faintly seen but too small to measure, a default value of 5 mm should be assigned (note: in case of a lymph node believed to be present and faintly seen but too small to measure, a default value of 5 mm should

be assigned in this circumstance as well). This default value is derived from the 5 mm CT slice thickness (but should not be changed with varying CT slice thickness).

**Lesions That Split or Coalesce on Treatment:** When non-nodal lesions ‘fragment’, the longest diameters of the fragmented portions should be added together to calculate the target lesion sum. Similarly, as lesions coalesce, a plane between them may be maintained that would aid in obtaining maximal diameter measurements of each individual lesion. If the lesions have coalesced such that they are no longer separable, the vector of the longest diameter in this instance should be the maximal longest diameter for the ‘coalesced lesion’.

### 3.2 Evaluation of Non-target Lesions

While some non-target lesions may actually be measurable, they need not be measured and instead should be assessed only qualitatively at the time points specified in the protocol.

**Complete Response (CR):** Disappearance of all non-target lesions and normalization of tumor marker level. All lymph nodes must be non-pathological in size (< 10 mm short axis).

**Non-CR/Non-PD:** Persistence of one or more non-target lesion(s) and/or maintenance of tumor marker level above the normal limits.

**Progressive Disease (PD):** Unequivocal progression of existing non-target lesions. (Note: the appearance of one or more new lesions is also considered progression).

The concept of progression of non-target disease requires additional explanation as follows:

- *When the patient also has measurable disease:* To achieve ‘unequivocal progression’ on the basis of the non-target disease, there must be an overall level of substantial worsening in non-target disease such that, even in presence of SD or PR in target disease, the overall tumor burden has increased sufficiently to merit discontinuation of therapy. A modest ‘increase’ in the size of one or more non-target lesions is usually not sufficient to qualify for unequivocal progression status.
- *When the patient has only non-measurable disease:* To achieve ‘unequivocal progression’ on the basis of the non-target disease, there must be an overall level of substantial worsening such that the overall tumor burden has increased sufficiently to merit discontinuation of therapy. A modest ‘increase’ in the size of one or more non-target lesions is usually not sufficient to qualify for unequivocal progression status. Because worsening in non-target disease cannot be easily quantified (by definition: if all lesions are non-measurable) a useful test that can be applied when assessing patients for unequivocal progression is to consider if the increase in overall disease burden based on the change in non-measurable disease is comparable in magnitude to the increase that would be required to declare PD for measurable disease: i.e., an increase in tumor burden representing an additional 73% increase in ‘volume’ (which is equivalent to a 20% increase diameter in a measurable lesion). Examples include an increase in a pleural

effusion from ‘trace’ to ‘large’, an increase in lymphangitic disease from localized to widespread, or may be described in protocols as ‘sufficient to require a change in therapy’. If ‘unequivocal progression’ is seen, the patient should be considered to have had overall PD at that point.

### **3.3 New Lesions**

The appearance of new malignant lesions denotes disease progression. The finding of a new lesion should be unequivocal: i.e., not attributable to differences in scanning technique, change in imaging modality or findings thought to represent something other than tumor (for example, some ‘new’ bone lesions may be simply healing or flare of pre-existing lesions). This is particularly important when the patient’s baseline lesions show partial or complete response. For example, necrosis of a liver lesion may be reported on a CT scan report as a ‘new’ cystic lesion, which it is not.

A lesion identified on a follow-up study in an anatomical location that was not scanned at baseline is considered a new lesion and will indicate disease progression. An example of this is the patient who has visceral disease at baseline and while on study has a CT or MRI brain ordered which reveals metastases. The patient’s brain metastases are considered to be constitute PD even if he/she did not have brain imaging at baseline.

If a new lesion is equivocal, for example because of its small size, continued therapy and follow-up evaluation will clarify if it represents new disease. If repeat scans confirm that there is a new lesion, then progression should be declared using the date of the initial scan.

### **3.4 Tumor Markers**

Tumor markers alone cannot be used to assess objective tumor responses. If markers are initially above the upper normal limit, however, they must normalize in order for a patient to be considered as having attained a complete response.

## **4 EVALUATION OF BEST OVERALL RESPONSE**

### **4.1 Time Point Response**

A response assessment should occur at each time point specified in the protocol.

For patients who have measurable disease at baseline Appendix Table 1 provides a summary of the overall response status calculation at each time point.

**Appendix Table 1: Summary of the Overall Response Status Calculation (Time Point Response) - Patient with Target (+/-) Non-target Disease**

CR=complete response; NE=inevaluable; PD=progressive disease; PR=partial response; SD=stable disease

## 4.2 Missing Assessments and Inevaluable Designation

When no imaging/measurement is done at all at a particular time point, the patient is not evaluable (NE) at that time point. If only a subset of lesion measurements are made at an assessment, usually the case is also considered NE at that time point, unless a convincing argument can be made that the contribution of the individual missing lesion(s) would not change the assigned time point response. This would be most likely to happen in the case of PD.

### 4.3 Best Overall Response: all Timepoints

Best response determination in trials where confirmation of complete or partial response IS required: Complete or partial responses may be claimed only if the criteria for each are met at a subsequent time point as specified in the protocol. In this circumstance, the best overall response can be interpreted as in Appendix Table 2.

**Appendix Table 2: Best Overall Response When Confirmation of Complete Response and Partial Response Required**

Figure 1 consists of three panels showing the distribution of the number of nodes in a cluster. The x-axis for all panels is labeled 'NE' at the bottom. The left panel shows a distribution with a peak at 1 node. The middle panel shows a distribution with a peak at 2 nodes. The right panel shows a distribution with a peak at 3 nodes.

a: If a CR is truly met at first time point, then any disease seen at a subsequent time point, even disease meeting PR criteria relative to baseline, makes the disease PD at that point (since disease must have reappeared after CR). Best response would depend on whether minimum duration for SD was met. However, sometimes 'CR' may be claimed when subsequent scans suggest small lesions were likely still present and in fact the patient had PR, not CR at the first time point. Under this circumstance, the original CR should be changed to PR and the best response is PR.

point. Under these circumstances, the original CR should be changed to PR and the best response is PR.

#### 4.4 Special Notes on Response Assessment

When nodal disease is included in the sum of target lesions and the nodes decrease to ‘normal’ size (< 10 mm), they may still have a measurement reported on scans. This measurement should be recorded even though the nodes are normal in order not to overstate progression should it be based on increase in size of the nodes. As noted earlier, this means that patients with CR may not have a total sum of ‘zero’ on the case report form (CRF).

Patients with a global deterioration of health status requiring discontinuation of treatment without objective evidence of disease progression at that time should be reported as 'symptomatic deterioration'. Every effort should be made to document objective progression even after discontinuation of treatment. Symptomatic deterioration is not a descriptor of an objective response: it is a reason for stopping study therapy. The objective response status of such patients is to be determined by evaluation of target and non-target disease as shown in Appendix Table 1 and Table 2.

For equivocal findings of progression (e.g., very small and uncertain new lesions; cystic changes or necrosis in existing lesions), treatment may continue until the next scheduled

assessment. If at the next scheduled assessment, progression is confirmed, the date of progression should be the earlier date when progression was suspected.

## **5 ADDITIONAL CONSIDERATIONS**

### **5.1 Duration of Response**

*Duration of overall response:* The duration of overall response is measured from the time measurement criteria are first met for CR/PR (whichever is first recorded) until the first date that recurrent or progressive disease is objectively documented (taking as reference for progressive disease the smallest measurements recorded on study).

The duration of overall complete response is measured from the time measurement criteria are first met for CR until the first date that recurrent disease is objectively documented.

*Duration of stable disease:* Stable disease is measured from the start of the treatment (in randomized trials, from date of randomization) until the criteria for progression are met, taking as reference the smallest sum on study (if the baseline sum is the smallest, this is the reference for calculation of PD).

### **5.2 Lesions That Disappear and Reappear**

If a lesion disappears and reappears at a subsequent time point it should continue to be measured. However, the patient's response at the point in time when the lesion reappears will depend upon the status of his/her other lesions. For example, if the patient's tumour had reached a CR status and the lesion reappeared, then the patient would be considered PD at the time of reappearance. In contrast, if the tumour status was a PR or SD and one lesion which had disappeared then reappears, its maximal diameter should be added to the sum of the remaining lesions for a calculated response: in other words, the reappearance of an apparently 'disappeared' single lesion amongst many which remain is not in itself enough to qualify for PD: that requires the sum of all lesions to meet the PD criteria. The rationale for such a categorization is based upon the realization that most lesions do not actually 'disappear' but are not visualized because they are beyond the resolving power of the imaging modality employed.

### **5.3 Use of Fluorodeoxyglucose-Positron Emission Tomography**

While fluorodeoxyglucose-positron emission tomography (FDG-PET) response assessments need additional study, it is sometimes reasonable to incorporate the use of FDG-PET scanning to complement CT scanning in assessment of progression (particularly possible 'new' disease). New lesions on the basis of FDG-PET imaging can be identified according to the following algorithm:

- a) Negative FDG-PET at baseline, with a positive FDG-PET at follow-up is a sign of PD based on a new lesion. Confirmatory CT is recommended.
- b) No FDG-PET at baseline and a positive FDG-PET at follow-up:
  - If the positive FDG-PET at follow-up corresponds to a new site of disease confirmed by CT, this is PD.
  - If the positive FDG-PET at follow-up is not confirmed as a new site of disease on CT, additional follow-up CT scans are needed to determine if there is progression occurring at that site (if so, the date of PD will be the date of the initial abnormal FDG-PET scan).

If the positive FDG-PET at follow-up corresponds to a pre-existing site of disease on CT that is not progressing on the basis of the anatomic images, this is not PD.

## Appendix 2 Child-Pugh Score

Measure	1 point	2 points	3 points

KKD(US)	Kyowa Kirin Pharmaceutical Development, Inc.
KM	Kaplan-Meier
Max	maximum
MedDRA	Medical Dictionary for Regulatory Activities
Min	minimum
MSI	microsatellite instability
MTD	maximum tolerated dose
NSCLC	non-small-cell lung cancer
NSQ	non-squamous cell
ORR	overall response rate
OS	overall survival
PD	progressive disease
PD-L1	programmed cell death-ligand 1
PFS	progression-free survival
PR	partial response
PS	Performance status
PT	preferred term
QTcB	QT interval corrected using Bazett's formula

Abbreviations/Acroynms

QTcF	QT interval corrected using Fridericia's formula
RECIST v1.1	Response Evaluation Criteria in Solid Tumors version 1.1
SAE	serious adverse event
SCCHN	squamous cell carcinoma of the head and neck
SD	stable disease
Std Dev	standard deviation
SOC	system organ class
SQ	squamous cell
TEAE	treatment-emergent adverse event
TLF	tables, data listings, figures
TMTB	total measured tumor burden
TTR	time to response
WHO	World Health Organization

1 INTRODUCTION

This Statistical Analysis Plan (SAP) has been developed after review of Kyowa Kirin Pharmaceutical Development, Inc. Protocol 0761-014 (Amendment 2, dated 05 Dec 2016), along with the corresponding electronic case report forms (eCRF). This SAP describes the analysis sets and specific details for the statistical methods to be used for the analysis and reporting of all efficacy, safety, pharmacokinetic parameters, and immunogenicity data collected during the conduct of Protocol 0761-014. This SAP supersedes the statistical considerations identified in Protocol 0761-014 with regards to details of the analyses; where considerations are substantially different, they will be identified as such in this document. In the event that the protocol has amendment(s) that do not have an impact on the statistical analysis methodology, this SAP will not require an amendment. This SAP has been developed and finalized prior to database lock of the clinical database for Protocol 0761-014. If additional analyses are required to supplement the planned analyses described in this SAP, they may be performed and will be identified in the Clinical Study Report (CSR).

This SAP is being written with consideration of the recommendations outlined in the International Conference on Harmonization (ICH) E9 Guideline entitled “Guidance for Industry: Statistical Principles for Clinical Trials” and the most recent ICH E3 Guideline, entitled “Guidance for Industry: Structure and Content of Clinical Study Reports.”

2 OBJECTIVES

The objectives of this study are as follows:

2.1 Primary Objective

The primary objective of this study is to characterize the safety and tolerability and determine the maximum tolerated dose (MTD) or the highest protocol-defined dose in the absence of exceeding the MTD, of the combination regimen of mogamulizumab and nivolumab in subjects with locally advanced or metastatic solid tumors

2.2 Secondary Objectives

The secondary objective of this study is to evaluate the anti-tumor activity of the combination of mogamulizumab and nivolumab based on the Response Evaluation Criteria in Solid Tumors version 1.1 (RECIST v1.1). Anti-tumor activity will be assessed as overall response rate (ORR), time to response (TTR), duration of response (DOR), progression-free survival (PFS), and overall survival (OS).

2.3 Exploratory Objectives

The exploratory objectives of this study are:

- 1) To assess serum concentrations of mogamulizumab and nivolumab when administered in combination.
- 2) To evaluate the immunogenicity of mogamulizumab and nivolumab when administered in combination.
- 3) To evaluate the pharmacodynamic profile of the combination of mogamulizumab and nivolumab and determine which biomarkers may correlate with safety and/or anti-tumor activity.
- 4) To evaluate the ORR of the combination of mogamulizumab and nivolumab based on the immune-related RECIST (irRECIST) v1.1.

3 OVERALL STUDY DESIGN AND TREATMENT PLAN

This is a multicenter, Phase 1/2, open-label, dose-finding, cohort-expansion study of the anti-CCR4 antibody mogamulizumab in combination therapy with the anti-programmed death receptor-1 (PD-1) antibody nivolumab in adult subjects with locally advanced or metastatic solid tumors. The study includes a Phase 1 dose finding and a Phase 2 cohort expansion:

- Phase 1 dose finding has a 3+3 design that will identify the MTD or the highest protocol-defined dose, in the absence of exceeding the MTD, for the combination regimen and will enroll up to 12 subjects (3 to 6 subjects per cohort).
- Phase 2 cohort expansion will explore the safety, pharmacokinetic (PK), PD, and anti-tumor activity of the highest tolerated dose of the combination regimen and will enroll up to 184 subjects (21 to 36 per tumor type) in up to 7 tumor-specific expansion cohorts.

Phase 1: Dose-finding: The dose levels and schedules are described below:

Dose Level	Dosage of Mogamulizumab		Dosage of Nivolumab
	Cycle 1 (Days 1, 8, 15, 22)	Subsequent Cycles (Days 1, 15)	All Cycles (Days 1, 15)
1	1.0 mg/kg	1.0 mg/kg	240 mg
Optional ^a	0.3 mg/kg	0.3 mg/kg	240 mg

a: This dose level may be enrolled if > 1 subject experiences dose-limiting toxicity at Dose Level 1.

Phase 2: Cohort expansion

Up to 184 subjects (21 to 36 subjects per tumor type) with locally advanced or metastatic disease in the following tumor types will be enrolled: squamous cell non-small cell lung cancer (NSCLC); programmed cell death ligand 1 (PD-L1)-non-expressing non-squamous cell NSCLC; squamous cell carcinoma of the head and neck (SCCHN); colorectal carcinoma, non-microsatellite instability (non-MSI) high; ovarian cancer, hepatocellular carcinoma (HCC), and pancreatic adenocarcinoma. PD-L1 expressing is defined as membrane staining

observed in $\geq 1\%$ tumor cells among a minimum of 100 evaluable tumor cells. Subjects will be treated with the highest dose of the combination regimen that was considered tolerable in Phase 1. The safety and tolerability of the dosing regimen used in each expansion cohort will be monitored. The SRC will review cumulative safety data from all subjects approximately every 2 months during the enrollment period. Clinical safety in the expansion cohorts will be monitored continually.

4 STATISTICAL METHODOLOGY

This plan describes methods planned for the analysis and display of efficacy, safety, pharmacokinetic parameters, and immunogenicity endpoints. Separate plans will document exploratory analyses of pharmacokinetic/pharmacodynamic data, pharmacodynamic relationships with safety and/or efficacy results, and the effects of immunogenicity on safety, efficacy, pharmacokinetic and pharmacodynamic.

The specific endpoints are as follows.

Primary Endpoints:

- Safety and tolerability will be evaluated by assessing adverse events (AEs), changes in physical examination findings, vital sign measurements, 12-lead electrocardiogram (ECG) readings, and clinical laboratory evaluations.

Secondary Endpoints:

- Overall response will be evaluated using RECIST v1.1. Overall response rate is calculated based on the best overall response (BOR), defined as the best response designation recorded between the date of first dose of investigational medical product (IMP) and the date of subsequent anti-cancer therapy (excluding on-treatment palliative radiotherapy of non-target bone or CNS lesions). Note: Continuation of nivolumab after discontinuing combination therapy does not count as start of new therapy for this definition. A BOR of either complete response (CR) or partial response (PR) requires confirmation of the assessment at least 4 weeks later. In addition, as a sensitivity analysis, BOR will also be defined as the best response designation recorded between the date of first dose of IMP and the date of first objectively documented progression (i.e. radiographic progression) or the date of subsequent anti-cancer therapy (excluding on-treatment palliative radiotherapy of non-target bone or CNS lesions), whichever occurs first.
- Time to response (TTR): Days from Cycle 1 Day 1 to the first assessment date of confirmed CR/PR using RECIST v1.1.
- Duration of response (DOR): Days from the first assessment date of confirmed CR/PR to the date of death or progressive disease (PD), whichever is earlier, using RECIST v1.1.

For subjects who neither progress nor die, the duration of objective response will be censored at the same time they will be censored for the primary definition of PFS. DOR will be evaluated for responders (i.e. subjects with confirmed CR or PR) only.

- Progression-free survival (PFS): Days from Cycle 1 Day 1 to the date of death or PD using RECIST v1.1, whichever is earlier. Clinical deterioration in the absence of objectively documented progression per RECIST 1.1 is not considered progression for the purpose of determining PFS. Subjects who die without a reported progression will be considered to have progressed on the date of their death. Subjects who did not progress or die will be censored on the date of their last evaluable tumor assessment. Subjects who did not have any on study tumor assessments and did not die will be censored on the date of first dose. Subjects who started any subsequent anti-cancer therapy, including tumor-directed radiotherapy and tumor-directed surgery, without a prior reported progression will be censored at the last evaluable tumor assessment prior to initiation of the subsequent anti-cancer therapy. For subjects whose BOR is PR or CR using RECIST v1.1, the date of first documented objective tumor progression or death that occurs after the last documented PR or CR will be used as the PFS event date.
- Overall survival (OS): Days from Cycle 1 Day 1 to the date of death. For subjects without documentation of death, OS will be censored on the last date the subject was known to be alive.

Exploratory Endpoints

- Pharmacokinetic parameters:
 - Mogamulizumab: observed minimum serum concentration at the end of a dosing interval (C_{\min}) and corresponding C_{\max} ; and
 - Nivolumab: C_{\min} .
- Immunogenicity: Anti-mogamulizumab antibody and anti-nivolumab antibody;
- Pharmacodynamic parameters: biomarkers may include, but are not limited to, immune cell subsets and factors such as cytokines and chemokines in tumor and/or blood;
- Immune-related overall response evaluated using irRECIST v1.1.

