### **8.5.1 Permitted Concomitant Medications**

Subjects may receive medications to treat pre-existing conditions, IMP-related AEs, or IMP-unrelated AEs.

Subjects are permitted the use of topical, ocular, intra-articular, intranasal, and inhalational corticosteroids (with minimal systemic absorption). Adrenal replacement steroids are permitted. A brief (less than 3 weeks) course of corticosteroids for prophylaxis (e.g., contrast dye allergy) or for treatment of non-autoimmune conditions (e.g., delayed-type hypersensitivity reaction caused by a contact allergen) is permitted.

Immunosuppressive agents including steroids may be used to treat IMP-related AEs, as described in Section [8.2](#).

Concomitant palliative and supportive care for disease-related symptoms (including bisphosphonates and RANK-L inhibitors) is allowed if initiated prior to the first dose of study therapy.

The potential for overlapping toxicities with radiotherapy and the IMPs currently is not known. Therefore, palliative radiotherapy is not recommended while receiving IMPs. If palliative radiotherapy is required, then IMP should be withheld for at least 1 week before, during and 1 week after radiation. Subjects should be closely monitored for any potential toxicity during and after receiving radiotherapy, and AEs considered related to radiotherapy should resolve to Grade  $\leq 1$  prior to resuming IMP. Only non-target bone lesions without lung tissue included in the planned radiation field or CNS lesions may receive palliative radiotherapy while on study treatment.

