PR	NE	SD provided minimum criteria for SD duration was met, otherwise, NE
NE	NE	NE

a: If a CR is truly met at first time point, then any disease seen at a subsequent time point, even disease meeting PR criteria relative to baseline, makes the disease PD at that point (since disease must have reappeared after CR). Best response would depend on whether minimum duration for SD was met. However, sometimes ‘CR’ may be claimed when subsequent scans suggest small lesions were likely still present and in fact the patient had PR, not CR at the first time point. Under these circumstances, the original CR should be changed to PR and the best response is PR.

CR=complete response; NE=not evaluable; PD=progressive disease; PR=partial response; SD=stable disease.

Time to Response (TTR)

Time to response will only be summarized descriptively for responders (i.e., CR or PR).

Duration of Response (DOR)

Duration of response will be calculated from the first date of confirmed CR/PR to the date of death or the date of first documented tumor progression (PD), whichever is earlier, using RECIST v1.1. Subjects who remain alive and do not progress will be censored on the date of their last tumor assessment. Subjects who start subsequent therapy without a prior PD will be censored at the last tumor assessment prior to initiation of the subsequent anticancer therapy. Response duration will only be evaluated in subjects with a BOR of CR or PR.

The median DOR, along with its two-sided 95% CI (Brookmeyer, 1982), will be estimated using the Kaplan-Meier (KM) method.

Progression-Free Survival (PFS)

PFS will be calculated as the number of days from the first dose of IMP to the date of death or PD, whichever is earlier. For subjects whose BOR is PR or CR using RECIST v1.1, the date of first documented objective tumor progression or death that occurs after the last documented PR or CR, and prior to the start of post-treatment anti-cancer therapy will be used as the PFS event date. Subjects who die without a reported prior progression will be considered to have progressed on the date of their death. Subjects who remain alive and do not progress will be censored on the last tumor assessment date. Subjects who start subsequent therapy without a prior reported progression will be censored on the date of last tumor assessment prior to initiation of subsequent anticancer therapy. Subjects who have no post-baseline tumor assessments and do not die will be censored on Day 1.

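### The PFS and DOR censoring rules omit the palliative-radiotherapy exemption that BOR carries, and they conflict with the SAP's own post-treatment wording

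*SAP*

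**What the plan says.** **Permitted radiotherapy.** Protocol 8.5.1 advises against palliative radiotherapy during treatment but allows a limited form: "Only non-target bone lesions without lung tissue included in the planned radiation field or CNS lesions may receive palliative radiotherapy while on study treatment". Under Protocol Table 9-1, scans are at Week 10 and then at least every 12 weeks until unequivocal progression or death.

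**BOR.** In SAP Section 4 the window closes at subsequent anti-cancer therapy, "excluding on-treatment palliative radiotherapy of non-target bone or CNS lesions". Protocol 10.1 has the same exemption. A CR or PR "requires confirmation of the assessment at least 4 weeks later".

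**PFS.** SAP Section 4: "Subjects who started any subsequent anti-cancer therapy, including tumor-directed radiotherapy and tumor-directed surgery, without a prior reported progression will be censored". The date used is the "last evaluable tumor assessment prior to initiation of the subsequent anti-cancer therapy". There is no exemption.

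**DOR.** SAP Section 4 defines it as "Days from the first assessment date of confirmed CR/PR to the date of death or progressive disease (PD), whichever is earlier". When neither event has occurred, "the duration of objective response will be censored at the same time they will be censored for the primary definition of PFS". SAP 4.9.1 adds: "Subjects who start subsequent therapy without a prior PD will be censored at the last tumor assessment prior to initiation". Again there is no exemption.

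**Other wording in the SAP.** The responder PFS rule in 4.9.1 counts a progression or death after the last CR or PR if it comes before post-treatment anti-cancer therapy. The notes to Listings 16.2.6.2.1 (PFS) and 16.2.6.3.1 (TTR and DOR) likewise take the last tumor assessment before post-treatment therapy.

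**The concern.** The same permitted event, palliative radiotherapy during study treatment, leaves the BOR window open but appears to end follow-up for PFS and DOR. A subject who stays on both drugs and keeps being scanned would leave the PFS and DOR analyses at the previous scan.

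Two things are at stake. First, the scan that confirms a response can fall after the date on which the duration of that response is censored. DOR is summarised only for all cancer types together because responders are few (Table 14.2.3.1 footnote), and duration of response is among the observations considered at the Stage 1 review (SAP 4.2 and 4.9.2.2). Second, a need for palliative radiotherapy may signal approaching progression. Censoring on it would then be informative and would tend to raise the PFS curve.

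**Working it through.** The documents state no PFS or DOR figure to reproduce. The check applies the SAP's rules to the protocol's scan schedule.

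**1. Does the PFS and DOR term include permitted radiotherapy?** The BOR text has to carve palliative radiotherapy out of subsequent anti-cancer therapy, which suggests that the unqualified term includes it. The PFS sentence then names tumor-directed radiotherapy. The PFS and DOR definitions in Protocol 10.1 have no therapy-censoring rule, so the SAP introduced this one without carrying the exemption across.

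**2. DOR for one responder.** PR at Week 10, permitted radiotherapy at Week 14, PR confirmed at Week 22 (12 weeks later, so the 4-week minimum is met), no progression or death. Listing 16.2.6.3.1 gives DOR = end date − response date + 1; SAP 6.2.1 gives months = days / 30.4.
- Section 4 rule: the last scan before radiotherapy is Week 10, so DOR = 0 + 1 = 1 day (0.03 months), censored.
- With the exemption, last scan Week 22: 12 × 7 + 1 = 85 days (2.80 months).
- With the exemption, last scan Week 34: 24 × 7 + 1 = 169 days (5.56 months).

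Starting DOR at the confirmation date does not rescue the rule: 70 − 154 + 1 = −83 days.

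**3. A responder who is irradiated and later progresses on treatment.**
- PFS: the therapy sentence in Section 4 censors, because no progression preceded the radiotherapy. The responder rule, in Section 4 and again in 4.9.1, gives an event at the progression date.
- DOR: Section 4 applies PFS censoring only to subjects who neither progress nor die, so this subject has an event. The therapy sentence in 4.9.1 censors.

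Two programmers could follow the SAP and get different results.

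**4. Direction of the PFS effect (assumed inputs).** Among subjects progression-free at Week 10, let a share f be irradiated before Week 22. Let q be the proportion of the others who progress by Week 22, and r the proportion of the irradiated who do.
- True conditional PFS = (1 − f)(1 − q) + f(1 − r).
- Reported with irradiated subjects censored = 1 − q.
- Difference = f(r − q).

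With q = 50% and r = 80%:
- f = 5%: 0.95 × 0.5 + 0.05 × 0.2 = 48.5%, against 50.0% reported.
- f = 10%: 0.90 × 0.5 + 0.10 × 0.2 = 47.0%, against 50.0%.
- f = 20%: 0.80 × 0.5 + 0.20 × 0.2 = 44.0%, against 50.0%.

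If r = q the difference is zero. A Kaplan-Meier simulation (exponential PFS, 18-week median, radiotherapy always within the 12 weeks before progression) agrees on direction. At Week 22 the true value is about 43%, against 44%, 45%, 48% and 52% when 5%, 10%, 20% and 30% are irradiated. That timing assumption makes the censoring strongly informative by construction.

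**The case against.** The best counter-argument is that the SAP already intends the sensible rule. The PFS and DOR listings carry a column for post-treatment therapy, the supporting Listing 16.2.4.9 covers therapy after treatment discontinuation, and Protocol 8.5.2 counts radiation as prohibited anti-neoplastic therapy only when it is extensive and not palliative. On that view the BOR parenthesis is a clarification. The Table 14.2.3.1 footnote also describes a single assessment window for the primary DOR method, so the 1-day result needs one term to mean different things for BOR and DOR.

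This stands in part. It rules out saying that the SAP has settled on censoring at permitted radiotherapy. It does not remove the Section 4 sentence, which names radiotherapy without exemption, or the 4.9.1 sentences that repeat the rule unqualified. The different meaning for BOR and DOR is what the Section 4 text produces.

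Other limits also stand:
- Only subjects irradiated without a prior reported progression are affected. A new CNS lesion is already progression under Protocol Appendix 1.
- The 1-day case needs radiotherapy between the first response scan and the next scan.
- Precision is low. If half of the largest cohort (36) were progression-free at Week 10, 10% of those 18 is about two subjects, and the 95% margin at 50% is 1.96 × √(0.25/18), roughly ±23 points.
- Irradiating a non-target lesion may mask its progression, so following subjects through radiotherapy can also favour PFS. A stricter PFS rule is a defensible choice if stated consistently.

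**Conclusion.** The inconsistency is real and worth correcting. PFS and DOR lack the exemption that BOR has, and the SAP uses two different triggers for censoring. For an affected responder the choice decides between a censored value of 1 day and at least 85 days, or between a censored observation and an event. The DOR result follows from the SAP's rules and the scan schedule for the stated example, without any assumed rate.

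A reader might infer three stronger things that the documents do not support:
- *That PFS will be materially biased upward.* The direction is plausible, but no radiotherapy frequency or progression risk is given. The percentages above are illustrations; the size is unknown and probably small.
- *That a responder would be reported as having a 1-day response.* The value is censored and adds almost nothing to a Kaplan-Meier estimate. The cost is lost follow-up.
- *That radiotherapy before Week 10 means censoring on Day 1.* The SAP states Day 1 censoring for subjects with no post-baseline scan who do not die; it is a natural convention, but not a stated rule, for subjects scanned later.

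PFS and DOR are secondary and descriptive. No sample size, error rate, Simon boundary or primary safety conclusion changes, and the BOR exemption already protects the response rate.

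**What to change.** 1. Add the BOR parenthesis, "excluding on-treatment palliative radiotherapy of non-target bone or CNS lesions", to the PFS and DOR therapy-censoring sentences in SAP Sections 4 and 4.9.1.
2. Use one defined term for the therapy that censors. Align subsequent and post-treatment across Section 4, the responder PFS rule in 4.9.1 and the notes to Listings 16.2.6.2.1 and 16.2.6.3.1. State which sentence governs a responder who is irradiated and later progresses.
3. Keep censoring at any tumor-directed radiotherapy as a sensitivity analysis for PFS and DOR.

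The cost is a few phrases before database lock and one extra run of two tables; the scans and therapy dates are already collected. PFS may come out slightly less favourable. Irradiation may also mask progression of a non-target lesion, and the sensitivity analysis would show how much the choice of rule matters.
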